9.2 Sample size determination

To characterise the shape of the curve for the dose-response relationship it is considered adequate to test 3 doses of oral NNC0385-0434 and the sample size for each dose is determined in order to achieve a sufficient precision on this relationship. Furthermore, sample size calculation is done for analyses addressing the primary estimand. Here, measurements of the primary endpoint from patients that have discontinued treatment prematurely but continuing in the trial (retrieved dropouts) are treated as missing.

In the sample size calculations addressing the primary estimand, missing values and assessments from retrieved dropouts are assumed to be similar to treatment completers within the same treatment group.

The sample size calculation assumes at least 45 eligible measurements of the primary endpoint in each treatment arm (eligible assessment defined as non-missing and obtained during the on-treatment observation periods, see Section [9.3](#) for definition of the on-treatment observation period). The sample size calculation assumes an SD of 30%-points for the percent change in LDL-C from baseline to week 12.

Data from the currently approved PCSK9 inhibitors are as follows:

- Alirocumab: lowering percentage LDL-C after 24 weeks by 61 percent with SE=0.7 for n=1530, corresponding to an SD of 27%-points²¹
- Evolocumab: lowering percentage LDL-C after 52 weeks by 46.8 percent with SE=3.0 for n=126, corresponding to an SD of 34%-points²²

[Table 9-1](#) includes different scenarios for the probability of the 95% confidence interval for the treatment difference to have the given halfwidth for different scenarios of number of patients per treatment arm.

A standard deviation of 30%-points and at least 45 eligible measurements in each treatment arm will allow the 95% confidence interval for the estimated difference between an oral NNC0385-0434 dose and the placebo group, with 94% probability, to be contained within $\pm 14\%$ -points of the estimate. This is considered to be a sufficient precision for determining which doses to use for the continued development of oral NNC0385-0434.

The calculations in [Table 9-1](#) also apply for the comparison between oral doses of NNC0385-0434 and s.c. evolocumab.

In total this requires a sample size of 255 patients.

Table 9-1 Probability of desired CI half-width

N per active arm/N for placebo group (Eligible)	SD (%-points)	CI half-width (%-points)	Probability
51 (45)	30	14	94%

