5.3.2 Main analytical approach

The primary estimand for percent change in LDL-C addresses the efficacy of oral NNC0385-0434 and will be estimated based on the FAS using the on-treatment observation period.

The primary analysis for the primary estimand for percent change in LDL-C is an analysis of covariance (ANCOVA) with randomised treatment (each oral NNC0385-0434 dose, pooled placebo group, and s.c. evolocumab) and strata as factors (population strata (inclusion criteria 3a/3b), country (Japan/non-Japan)) and baseline LDL-C as a covariate.

The estimated treatment difference between individual oral NNC0385-0434 doses and placebo will be reported together with the associated two-sided 95% CI and corresponding two-sided p-value.

Handling of missing week 12 values for the primary estimand

The primary estimand will be estimated based on the FAS using post-baseline measurements up to and including week 12 from the on-treatment observation period. Missing data and observations outside the on-treatment observation period such as week 12 assessments for retrieved dropouts will be imputed using multiple imputation assuming missing at random (MAR). Missing post-baseline data will be imputed sequentially within each treatment using the observed post-randomisation assessments for visits prior to the one in question obtained during the on-treatment observation period. The proportion of missing LDL-C change data at week 12 is assumed to be no more than 10% and is expected to be similar in all treatment arms.

The multiple imputation is done in three steps:

1. Imputation:

- a. Intermittent missing values are imputed using a Markov Chain Monte Carlo (MCMC) method, in order to obtain a monotone missing data pattern. This imputation is done for each of the treatment groups separately and 1000 copies of the dataset will be generated.
- b. A sequential regression approach for imputing monotone missing values at planned visits will be implemented starting with the first visit after baseline and sequentially continuing to the last planned visit at week 12. A model used to impute missing values at each planned visit will be fitted for each of the treatment groups (each NNC0385-0434 dose, evolocumab or pooled placebo) using observed data. The imputation model will include strata as factors (population strata (inclusion criteria 3a/3b), country (Japan/non-Japan)) and baseline and post-baseline LDL-C values prior to the visit in question as covariates.

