2. Analysis: An ANCOVA with treatment and strata (population strata (inclusion criteria 3a/3b), country (Japan/non-Japan)) as factors and baseline LDL-C as a covariate will be used to analyse LDL-C % change at week 12 for each of the 1000 complete data sets generated as part of the imputation of missing values.

3. Pooling: Rubin's rule will be used to combine the analysis results in order to draw inference.

Analyses addressing the additional estimand

The analysis model for percent change in LDL-C is an ANCOVA with randomised treatment and strata as factors (population strata (inclusion criteria 3a/b), country (Japan/non-Japan)) and baseline LDL-C as a covariate.

The estimated treatment difference between individual oral NNC0385-0434 doses and placebo will be reported together with the associated two-sided 95% CI and corresponding two-sided p-value.

Handling of missing week 12 values for the additional estimand

The additional estimand will be estimated based on the FAS using week 12 measurements from the in-trial observation period. Missing week 12 data will be imputed using multiple imputation assuming missing at random (MAR). In case of sparse data in some of the groups, a common treatment discontinuation group across treatments will be created and randomised treatment will be added to the model as factor. If this is still not sufficient, the model will be thinned in the following order, starting with the one that will be removed first; strata, randomised treatment, and baseline value.

The multiple imputation approach is done in three steps:

1. Imputation: Imputation will be done within groups defined by randomised treatment and treatment status at week 12. The imputation model will include strata as factors (population strata (inclusion criteria 3a/3b), country (Japan/non-Japan)) and baseline LDL-C as a covariate. The estimated posterior distribution for the parameters (regression coefficients and variances) in the imputation models are then used to impute missing week 12 LDL-C values. This will be done 1000 times, resulting in 1000 complete data sets.

2. Analysis: Analysis of each of the 1000 complete data sets using the ANCOVA with randomised treatment and strata as factors (population strata (inclusion criteria 3a/b), country (Japan/non-Japan)) and baseline LDL-C as a covariate, resulting in 1000 estimates for each treatment.

3. Pooling: Rubin's rule will be used to combine the analysis results in order to draw inference.

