Analysis addressing the effect of oral NNC0385-0434 vs. s.c. evolocumab

This analysis will evaluate the treatment difference between individual oral NNC0385-0434 doses and s.c. evolocumab using the same analysis as the primary analysis for the primary estimand described above. However, the treatment differences with 95% confidence intervals between oral NNC0385-0434 doses and s.c. evolocumab will be estimated but no confirmatory testing will be carried out.

Dose-response modelling

In order to evaluate the effect of oral NNC0385-0434 dose vs. placebo on percent change in LDL-C and to characterise the dose-response relationship the mean percent LDL-C change will be estimated using dose as a continuous variable.

The dose-response candidate models in [Table 3](#) will be fit.

Table 3 Dose-response candidate models

Model	Functional form $f(d, \theta)$
E_{max}	$E_0 + E_{max} \frac{d}{ED_{50} + d}$
Linear	$E_0 + \beta d$

E_0 : the expected effect on LDL-C when treated with placebo, ED_{50} : The dose, which produces half of E_{max} , E_{max} : Maximum effect attributable to the drug, d : NNC0385-0434 dose.

The candidate models will be fit to the estimated percent change in LDL-C means at week 12 for the employed oral NNC0385-0434 doses and placebo from the primary analysis model described above. Thus, all patients in the FAS will be included and the same assumptions regarding missing values and the impact of explanatory variables will be applied.

The model used to evaluate dose-response will be selected among the candidate models based on the best fit to data. The best fit will be evaluated based on convergence, model complexity, Akaike information criterion (AIC) value and visual evaluation.

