5.3.3 Sensitivity analysis

A sensitivity analysis will evaluate the treatment difference between individual oral NNC0385-0434 doses and placebo using the same analysis as the primary analysis for the primary estimand described above, but with baseline LDL-C not included as a covariate in the model.

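### Does the five-group ANCOVA need arm-specific residual variances for its pairwise confidence intervals to be valid?

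*SAP*

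**What the plan says.** SAP 5.3.2 defines the primary analysis as one model for all five treatment groups: "The primary analysis for the primary estimand for percent change in LDL-C is an analysis of covariance (ANCOVA) with randomised treatment". The analysis step for each imputed data set repeats it: "An ANCOVA with treatment and strata (population strata (inclusion criteria 3a/3b), country (Japan/non-Japan)) as factors and baseline LDL-C as a covariate will be used" for week-12 percent change. Rubin's "rule will be used to combine the analysis results in order to draw inference". Protocol 9.4.2 gives the same model, and SAP sections 1 and 6.2 declare no departure from the protocol.

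The evolocumab contrasts are obtained "using the same analysis as the primary analysis for the primary estimand described above. However, the treatment differences with 95% confidence intervals", without confirmatory testing. The one sensitivity analysis, in SAP 5.3.3, repeats the primary analysis "but with baseline LDL-C not included as a covariate in the model".

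The sample size calculation in Protocol 9.2 "assumes an SD of 30%-points for the percent change in LDL-C from baseline to week 12", the same for every arm. It cites two external results in support: an alirocumab trial at 24 weeks, "corresponding to an SD of 27%-points", and an evolocumab trial at 52 weeks, "corresponding to an SD of 34%-points".

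**The concern.** A least-squares ANCOVA estimates one residual variance. With five groups of equal size, that estimate is close to the average of the five arm variances, while the true variance of a two-arm contrast depends only on the two arms compared. Equal group sizes protect a two-group comparison from unequal variances, but they do not protect a pairwise contrast whose variance is borrowed from three other groups. If arm SDs differ, a nominal 95% CI can be too short or too long.

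CI width matters in this trial. Protocol 9.2 regards an interval within ±14 %-points as precise enough for choosing doses, and applies the same calculation to evolocumab. If placebo and 15 mg had SD 34 and the other three arms 27, the pooled interval for 15 mg against placebo would be within ±14 in 99% of trials, whereas a correctly sized interval would be so in 43%. The only planned sensitivity analysis leaves the error structure unchanged, so nothing in the plan would reveal this. The imputation models, by contrast, are fitted separately in each treatment group.

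**Working it through.** **Inputs.** 45 eligible measurements per arm and SD 30 (Protocol 9.2); 51 patients in each active arm and in pooled placebo (Protocol 4.1); predicted LDL-C reductions of 28, 46 and 60% (Protocol 4.3). The external SDs follow from the cited standard errors: 0.7 × √1530 = 27.4 and 3.0 × √126 = 33.7.

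**1. The plan's own figure.** The half-width is t(0.975, df) × S × √(2/n), where df × S²/SD² is chi-square with df degrees of freedom.

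- Two-arm variance, df = 2 × 45 − 2 = 88: expected size 1.987 × 30 × √(2/45) = 12.57; P(at most 14) = 93.7%, against 94% in Table 9-1.
- Five-arm ANCOVA, df = 225 − 5 − 2 − 1 = 217 (five groups, two strata factors, baseline): 1.971 × 30 × √(2/45) = 12.47; P(at most 14) = 99.5%.

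Table 9-1 therefore used two-arm degrees of freedom with one common SD. It did not assume unequal variances, and under that common SD the planned model does better than the table promises.

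**2. Effect of unequal SDs.** Ratio of the pooled to the true standard error = √(mean of the five arm variances ÷ mean of the two compared variances). Approximate coverage = 2Φ(1.96 × ratio) − 1. Assigning SDs to arms is an assumption throughout.

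| SDs: placebo/15/40/100/evolocumab | Contrast | Ratio | Coverage |
|---|---|---|---|
| 34/34/27/27/27 | 15 mg vs placebo | √(899.8/1156) = 0.882 | about 91.7% |
| 27/27/34/34/34 | 15 mg vs placebo | √(985.2/729) = 1.163 | 97.7% |
| 34/27/27/27/27 | any dose vs placebo | √(814.4/942.5) = 0.930 | 93.2% |
| 27/34/34/34/34 | any dose vs placebo | √(1070.6/942.5) = 1.066 | 96.3% |
| 32/28/28/28/28 | any dose vs placebo | √(832/904) = 0.959 | 94.0% |
| 28/32/32/32/32 | any dose vs placebo | √(976/904) = 1.039 | 95.8% |

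Taking every assignment of 27, 30 and 34 to five arms gives 3⁵ = 243 sets and 6 × 243 = 1,458 contrasts. Coverage ranges from 91.6% to 97.7% with mean 94.97%; 61% lie within one point of 95%, 20% are below 94%, 19% above 96% and 4.9% below 93%. Errors occur in both directions, and the extremes need the two compared arms at one end of the range and the other three at the opposite end.

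**3. Effect on the superiority tests.** For a 28-point difference (15 mg, placebo change taken as zero), the standard error is 30 × √(2/45) = 6.32 and power is Φ(28/6.32 − 1.96) = 99.3%. At SD 34 the standard error is 7.17 and power 97.4% (97.2% with t on 88 df). Power for 46 and 60 points exceeds 99.9%.

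**4. Price of arm-specific variances if the SDs are equal.** The half-width grows from 12.47 to 12.57, about 0.8%. The estimate is also noisier, so P(at most 14) falls from 99.5% to 93.7% and P(at most 13) from 82% to 69%. In a simulation that added imputation and Rubin pooling (51 per arm, 6 missing, 50 imputations, assumed baseline distribution and visit correlation), P(at most 14) fell from 94% to 83–84%. That last result depends on its assumed inputs and carries less weight.

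**The case for a change.** The strongest argument is that spread may grow with effect. The on-treatment period ends 58 days after last dose, so a patient who stops on or after day 84 − 58 = 26 can still supply a week-12 value to the primary analysis while losing drug effect. The additional estimand keeps all discontinuers. A mixture of on-drug and off-drug patients widens the active arms and not placebo.

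Suppose 10% of each arm has fully lost an effect of size Δ, with base SD 30. The arm variance is then 900 + 0.1 × 0.9 × Δ². With Δ = 0, 28, 46, 60 and 60, the last being the approximate figure for marketed antibodies in Protocol 2.2, the variances are 900, 971, 1090, 1224 and 1224, with mean 1082; the SDs are about 30/31/33/35/35.

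- Against placebo, the ratios for 15, 40 and 100 mg are √(1082/935) = 1.075, √(1082/995) = 1.043 and √(1082/1062) = 1.009. Coverage is 96.5%, 95.9% and 95.2%.
- For 100 mg against evolocumab, the ratio is √(1082/1224) = 0.940 and coverage 93.5%.

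On this mechanism the tested contrasts are slightly conservative. The shortfall falls on a contrast that is estimated only and amounts to 1.5 points.

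Several observations stand: the SAP names no variance structure, no analysis relaxes equal variance, and an arm-specific interval holds 94.9–95.1% coverage in the simulated complete-data sets. A group-specific-variance or robust-standard-error sensitivity analysis would be a reasonable optional addition. None of this shows that the specified model is wrong.

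**Conclusion.** The concern does not hold. ANCOVA without further qualification means one residual variance, so the model is fully specified and agrees with the common SD of 30 on which the trial was sized. The values 27 and 34 describe two different active drugs in different trials at weeks 24 and 52. They show variation between trials, give no placebo SD, and are no evidence that arms of this trial will differ.

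Even if that range is imposed on the arms, coverage averages 94.97%, and the worst case, 91.6%, needs an extreme pattern. Superiority conclusions would rarely change, the evolocumab contrasts carry no test, and ±14 points is a planning target, not an analysis rule. Dose selection also draws on the dose-response modelling and the exposure-response analyses.

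Replacing the protocol-specified primary model would trade a certain loss of precision under the protocol's own assumption (99.5% to 93.7% for a half-width of at most 14) for protection against a heterogeneity that the documents do not show. Experienced statisticians may choose either way. This conclusion assumes about 45 eligible values per arm and arm SDs not far outside 27 to 34; a much wider spread would make the pooled intervals less accurate, but nothing in the documents points to one.

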- Oral placebo (size-matched to oral NNC0385-0434 40 mg)
- Oral NNC0385-0434 100 mg
- Oral placebo (size-matched to oral NNC0385-0434 100 mg)
- S.c. evolocumab

Randomisation will be stratified according to participation in the PK sub-study, country and population (inclusion criteria a/b). Within each stratum, each patient will be randomly allocated to one of the treatment arms. For the main statistical analyses, the 3 placebo arms will be pooled into one placebo group.

Key inclusion criteria

- Male patient or female patient of non-childbearing potential.
- Established atherosclerotic cardiovascular disease (ASCVD) (criteria a) or ASCVD risk (criteria b):
 - a) Age ≥ 40 years at the time of signing informed consent and history of ASCVD
 - b) Age > 50 years at the time of signing informed consent and with ASCVD risk
- Serum LDL-C ≥ 1.8 mmol/L (≥ 70 mg/dL) as measured by the central laboratory at screening.
 - Japanese patients: Serum LDL-C ≥ 2.6 mmol/L (≥ 100 mg/dL) for patients of ≥ 40 years of age and with a history of coronary heart disease, and serum LDL-C ≥ 3.1 mmol/L (≥ 120 mg/dL) for all other Japanese patients
- Patients must be on maximally tolerated dose of statins.
- Patients not receiving statin must have documented evidence of intolerance to all doses of at least two different statins.

Key exclusion criteria

- Treatment with PCSK9i therapy (alirocumab or evolocumab within 90 days prior to screening) or PCSK9 siRNA therapy (inclisiran within 12 months prior to screening).
- Fasting triglyceride > 4.52 mmol/L (> 400 mg/dL) as measured by the central laboratory at screening.
- Myocardial infarction, stroke, hospitalization for unstable angina pectoris or transient ischaemic attack within 180 days prior to the day of screening.
- Renal impairment with eGFR < 30 ml/min/1.73 m² as measured by the central laboratory at screening.

Number of patients:

Approximately 255 patients will be randomly assigned to trial product. Out of the 255 patients, 30 Japanese and 30 non-Japanese patients will be randomised to the PK-sub-study.

Treatment groups and duration:

The total trial duration for an individual patient will be approximately 22 weeks divided into the following periods:

- Screening: up to 2 weeks
- Treatment period: 12 weeks
- Follow-up period: 7 weeks and 4 days

The following trial products will be supplied by Novo Nordisk for the duration of the trial:

- NNC0385-0434 A 15 mg, oral, once daily
- NNC0385-0434 A 40 mg, oral, once daily

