9.1 Statistical hypotheses

Confirmation of superiority for each oral NNC0385-0434 dose vs. placebo (pooled from all 3 placebo arms) will be evaluated using a hierarchical testing procedure starting with the treatment difference between the highest oral NNC0385-0434 dose (100 mg) and placebo and ending with the lowest dose (15 mg). In case of a non-significant treatment difference the testing procedure will stop. This will protect the family-wise type 1 error in the strong sense on a 5% level of significance.

The superiority test for oral NNC0385-0434 vs. placebo will be carried out as follows. Let $\mu_{NNC0385-0434,x}$ and $\mu_{placebo}$ denote the true mean of percent change in LDL-C from baseline for dose level x of oral NNC0385-0434 and placebo, respectively. The null and alternative hypotheses tested are

$$H_0: \mu_{NNC0385-0434,x} \geq \mu_{placebo} \text{ vs. } H_A: \mu_{NNC0385-0434,x} < \mu_{placebo}$$

The null hypothesis will be rejected if the upper limit of the estimated two-sided 95% CI for the treatment difference is below 0.

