5.1 General considerations

5.1.1 Handling of missing baseline data

The last available and eligible observation at or before randomisation is used as the baseline value. If no assessments are available, the mean value at randomisation across all patients is used as the baseline value.

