5.4.2 Supportive secondary endpoints

The following supportive secondary endpoints

- change in total cholesterol
- change in HDL-cholesterol
- change in VLDL-cholesterol
- change in triglycerides
- change in total Apo B
- change in total Apo CIII

are computed similar as the primary endpoint, that is for each of these six lipid/lipoprotein parameters, the percentual change from randomisation at week 0 to week 12 is defined as:

$$\% \text{ parameter change} = \frac{(\text{parameter value at week 12} - \text{parameter value at baseline})}{\text{parameter value at baseline}} \times 100\%$$

Each of these six endpoints will be analysed separately by an analysis of covariance (ANCOVA) with randomised treatment (each oral NNC0385-0434 dose, pooled placebo group, and s.c. evolocumab) and strata as factors (population strata (inclusion criteria 3a/3b), country (Japan/non-Japan)) and baseline parameter value as a covariate.

The parameter Lipoprotein a (Lp(a)) follows a log-normal distribution and will be log-transformed before analysis. The supportive secondary endpoint: Change in total Lp(a) (from baseline (week 0) to visit 9 (week 12)), will be reported as the result of the difference in log-transformed Lp(a) back-transformed to the original scale, implying that log-treatment-differences are reported as treatment ratios. Confidence intervals for the treatment ratios will be calculated as exponential upper and lower limits for log-treatment difference confidence intervals.

Safety endpoints

The secondary endpoint Treatment-emergent adverse events (TEAE) is the number of AEs recorded during the on-treatment period (see [section 4](#) for the definition of the on-treatment period). All AEs will be coded using the most recent version of the Medical Dictionary for Regulatory Activities (MedDRA)

Summaries of TEAEs are presented as an overview including all AEs, serious AEs, AEs leading to withdrawal, AEs by severity, AEs by relation to treatment and outcome of AEs. Furthermore, summary tables based on system organ class and preferred term is made for:

- All TEAEs
- Serious TEAEs
- TEAEs evaluated to be probably or possibly related to the trial products
- TEAEs by severity
- Serious TEAEs evaluated to be probably or possibly related to the trial products

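### The lipid ANCOVAs adjust for one of two available pre-treatment laboratory values; adding the screening value would be a small, low-cost gain in precision

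*SAP*

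**What the plan says.** **Two readings.** Inclusion criterion 4 (Protocol 5.1) uses a central-laboratory LDL-C at screening. The triglyceride exclusion reads "Fasting triglyceride > 4.52 mmol/L (> 400 mg/dL) as measured by the central laboratory at screening" (Protocol 1.1; also 5.2). The endpoints are then defined from week 0. Screening lasts up to two weeks, and background lipid therapy must have been stable for at least 30 days before it, so the two readings are close to replicates. For the other lipids, the Lipids row of Protocol Table 1-1 carries nine marks. That fits visits 1, 2, 4, 6, 7, 8, 9, 9X and 10, but the column alignment is lost in the text available here.

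**One covariate.** SAP 5.1.1 defines baseline: "The last available and eligible observation at or before randomisation is used as the baseline value". The LDL-C ANCOVAs for both estimands (SAP 5.3.2, Protocol 9.4.2) contain treatment, the two strata factors and that single value; the model statement ends with "country (Japan/non-Japan)) and baseline LDL-C as a covariate". The six percent-change secondary endpoints use "baseline parameter value as a covariate" plus the same factors (SAP 5.4.2). Covariates for the Lp(a) model are not written out. The imputation models hold baseline and, for the primary estimand, earlier post-baseline values. The sensitivity analysis in SAP 5.3.3 removes baseline. None of these models includes the visit 1 value alongside the visit 2 value.

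**The concern.** Percent change puts the week 0 reading in the denominator, so assay and day-to-day noise in that one reading goes straight into the endpoint. The same noise blurs the covariate. A second pre-treatment reading lets the model separate noise from the patient's usual level, at no extra sampling and with no change to endpoint or estimand.

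The trial was sized on interval width, and the adjusted means feed the placebo contrasts, the evolocumab contrasts and the dose-response fit. What is at stake is the width of those intervals, not their validity.

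**Working it through.** **Inputs from the documents.** "The sample size calculation assumes an SD of 30%-points for the percent change in LDL-C from baseline to week 12" and "at least 45 eligible measurements of the primary endpoint in each treatment arm" (Protocol 9.2); a half-width limit of 14 %-points with a stated probability of 94% (Table 9-1); entry limits of LDL-C at least 1.8 mmol/L and triglycerides at most 4.52 mmol/L; expected LDL-C reductions of 28, 46 and 60% (Protocol 4.3).

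**Assumed, because the documents give nothing.** LDL-C: within-person log SD 0.08-0.15 (stretched to 0.20), between-person 0.25-0.35. Triglycerides: within-person 0.15-0.30, between-person 0.35-0.50, with small treatment effects.

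**Step 1: the plan's figure.** Half-width = t(0.975, 88) × 30 × √(2/45) = 12.57 %-points. P(half-width ≤ 14) = P[χ²(88) ≤ 88 × (14/12.57)²] = 93.7%, against 94% stated. All eight rows of Table 9-1 reproduce within 2 points. This is a two-sample calculation with no covariate.

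**Step 2: why a second reading helps.** If visit 1, visit 2 and week 12 are equally correlated (ρ), the residual variance is 1 − ρ² with one reading and (1 − ρ)(1 + 2ρ)/(1 + ρ) with two. The ratio is (1 + 2ρ)/(1 + ρ)²: 0.889 at ρ = 0.5 and 0.830 at ρ = 0.7. This is a best case, with no patient-to-patient variation in true response.

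**Step 3: LDL-C.** Response variation h, which no pre-treatment value explains, dilutes the gain to (V2 + h)/(V1 + h). Here V1 and V2 are the residual variances with visit 2 alone and with both visits. Percent change was simulated in five arms with the entry limit applied at screening. With within-person 0.12 and between-person 0.25, the SD is 11.5 unadjusted, 11.0 with visit 2 and 10.1 with both. Reaching an SD of 30 needs h = 30² − 11.5² = 767.75. The ratio is then (102.01 + 767.75)/(121 + 767.75) = 0.979; direct simulation gave 0.980. For within-person 0.08-0.15 the simulated ratios were 0.968-0.989, and 0.976-0.993 in a separate run with 45 per arm and between-person 0.28. That is a variance cut of about 1-3%. Stretching to within-person 0.20 with between-person 0.35 gives 0.955.

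**Step 4: triglycerides.** The no-variation ratio r and the residual SD come from simulation. The last two columns are (r·V1 + h)/(V1 + h) with h = 20² and 30².

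| Within / between log SD | Residual SD, visit 2 only | r | +20 points | +30 points |
|---|---|---|---|---|
| 0.20 / 0.40 | 26.7 | 0.858 | 0.909 | 0.937 |
| 0.25 / 0.40 | 34.1 | 0.884 | 0.914 | 0.935 |
| 0.25 / 0.50 | 34.5 | 0.883 | 0.912 | 0.933 |
| 0.30 / 0.40 | 42.0 | 0.913 | 0.929 | 0.942 |
| 0.30 / 0.35 | 41.5 | 0.923 | 0.937 | 0.949 |

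With response variation the cut is about 5-9%. Without it the cut is about 8-14% in these rows, and reaches about 17% (ratio 0.83) only when within-person log SD is as low as 0.15.

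**Step 5: what this buys.** Interval width scales with the square root of the ratio.
- LDL-C: √0.99 = 0.995 and √0.97 = 0.985. If 30 is taken as the residual SD, the half-width goes from 12.57 to 12.51-12.38, a gain of 0.06-0.19 %-points. P(half-width ≤ 14) rises from 94% to about 95-96%. In patients per arm, 45 × (1/ratio − 1) = 0.5-1.4.
- Triglycerides: √0.95 = 0.975 and √0.91 = 0.954, so intervals are about 2.5-4.6% narrower, worth 2.4-4.5 patients per arm. At the 0.83 extreme they are 8.9% narrower, worth 9.2 patients.

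**Step 6: bias and cost.** Mean treatment estimates with and without the extra covariate differed by at most 0.12 %-points in simulation, so truncation of screening values by the entry limits did no visible harm. Residual degrees of freedom are 5 × 45 − (1 + 4 + 2 + 1) = 217, and one is spent.

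**The case against.** The strongest reply is that this hardly matters. On the primary endpoint the gain is under 0.2 of a 12.6-point half-width. Power against placebo at the smallest expected effect (28 points, SD 30, 45 per group) is already 99.3%. Table 9-1 relied on no covariate at all, so the planned adjustment already goes beyond what the sizing needed. The larger gain falls on triglycerides, a supportive endpoint with no test or precision target. The change is also more than one SAP sentence. Protocol 9.4.2 specifies the same model, and SAP 6.2 declares no departure from the protocol. The imputation models are fitted by arm, with about 30 × 3/15 = 6 Japanese patients in each. For the additional estimand they are also split by treatment status, where sparse data are already expected.

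All of this stands. It limits the point to a small improvement and shapes the fix. It does not remove the point, because the gain was positive in every scenario tried and the data are already collected.

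A reader might infer more: that the trial misses its precision target, that screening lipids are used only for eligibility, or that the lipid models ignore everything except baseline. The documents support none of these. The stated precision reproduces, the screening value becomes baseline when visit 2 is missing, and the strata are in the models. Nor is a full lipid panel at screening certain: LDL-C and triglycerides follow from the entry criteria, while the rest is read from the flowchart row.

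**Conclusion.** The planned ANCOVAs are valid. They leave a small amount of precision unused by adjusting for one of two pre-treatment readings. The variance cut available is about 1-3% for LDL-C at an SD of 30, and about 5-9% for triglycerides when true response varies between patients.

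A reader might take the 17% triglyceride figure as the expected gain. It requires no variation in true response and low within-person noise. The protocol's own LDL-C SD of 30 implies substantial response variation for that lipid, so assuming none for triglycerides would be uneven. VLDL-C may behave like triglycerides, but this was not checked.

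All sizes rest on assumed within-person and between-person variability. The ordering, small for LDL-C and larger for triglycerides, held throughout under the protocol's LDL-C SD.

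**What to change.** In SAP 5.3.2 and 5.4.2:
- Keep visit 2 as the baseline in the percent-change formula and as a covariate.
- Add the visit 1 value of the same parameter as a second pre-specified ANCOVA covariate wherever it was measured, on the log scale for Lp(a).
- If either pre-treatment value is missing, use the available one for both.
- Add the visit 1 value to the imputation models, and name it as the first term to drop when data are sparse, ahead of the existing thinning order.
- Say in SAP 5.3.3 that the sensitivity analysis leaves out both values.

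Make the matching change in Protocol 9.4.2, or record it as a change to the planned analyses in SAP 6.2, before unblinding. The cost is one degree of freedom out of about 217 and slightly larger imputation models. No extra sample or visit is needed, and endpoint, estimand and hypotheses are unchanged.
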